### **3. PATIENT SELECTION**

#### **3.1 Eligibility Criteria**

- 3.1.1 Patients must have histologically or cytologically confirmed locally advanced, recurrent or metastatic adenoid cystic carcinoma.
- 3.1.2 Patients must have measurable disease, defined as at least one lesion that can be accurately measured in at least one dimension (longest diameter to be recorded) as  $\geq 20$  mm by chest x-ray, as  $\geq 10$  mm with CT scan, or  $\geq 10$  mm with calipers by clinical exam. All tumor measurements must be recorded in millimeters (or decimal fractions of centimeters). See [section 10.1](#) for the evaluation of measurable disease.
- 3.1.3 Patients must have locally advanced and/or recurrent and/or metastatic disease not amenable to potentially curative surgery or radiotherapy. Any prior number of chemotherapy regimens is allowed. A minimum of at least 4 weeks since prior chemotherapy or radiation therapy should have elapsed, 6 weeks if the last regimen included BCNU or mitomycin C.
- 3.1.4 Age  $\geq 18$  years. Because no dosing or adverse event data are currently available on the use of vorinostat in patients  $< 18$  years of age, children are excluded from this study but will be eligible for future pediatric single-agent trials, if applicable.
- 3.1.5 Life expectancy of greater than 12 weeks.

3.1.6 ECOG performance status 0–2 (Karnofsky  $\geq 60\%$ ; see [Appendix A](#)).

3.1.7 Patients must have normal organ and marrow function as defined below:

- leukocytes  $\geq 3,000/\text{mcL}$
- absolute neutrophil count  $\geq 1,500/\text{mcL}$
- platelets  $\geq 100,000/\text{mcL}$
- total bilirubin within normal institutional limits(WNL)
- AST(SGOT)/ALT(SGPT)  $\leq 2.5 \times$  institutional upper limit of Normal (ULN)
- creatinine within normal institutional limits

OR

creatinine clearance  $\geq 60 \text{ mL/min/1.73 m}^2$  for patients with creatinine levels above institutional normal

3.1.8 Eligibility of patients receiving any medications or substances known to affect or with the potential to affect the activity or pharmacokinetics of vorinostat will be determined following review of their case by the Principal Investigator.

3.1.9 No other diagnosis of malignancy unless non-melanoma skin cancer, carcinoma in situ of the cervix, or a malignancy diagnosed  $\geq 5$  years previously and currently with no evidence of disease. HOWEVER - if the patient has had a previously diagnosed Stage I/II malignancy of another type, consideration for recruitment may be made by the CTEP senior investigator after discussion with local PI and patient's physician

3.1.10 Confirmed availability of tumor tissue (either fresh or from paraffin block) from the primary tumor or metastatic site to be available to use on correlative studies (see [Section 8](#) for details).

3.1.11 The effects of vorinostat on the developing human fetus at the recommended therapeutic dose are unknown. For this reason and because HDAC inhibitors are known to be teratogenic, women of child-bearing potential and men must agree to use adequate contraception (hormonal or barrier method of birth control; abstinence) prior to study entry and for the duration of study participation. Should a woman become pregnant or suspect she is pregnant while participating in this study, she should inform her treating physician immediately.

- 3.1.12 Ability to understand and the willingness to sign a written informed consent document.
- 3.1.13 If the patient's tumor can be easily accessed, a pre-treatment biopsy will be mandatory.

## **3.2 Exclusion Criteria**

- 3.2.1 Patients who have had chemotherapy or radiotherapy within 4 weeks (6 weeks for nitrosoureas or mitomycin C) prior to entering the study or those who have not recovered from adverse events due to agents administered more than 4 weeks earlier. More than 21 days from major surgery should have elapsed before the first dose of the study drug.
- 3.2.2 Patients may not be receiving any other investigational agents or have received vorinostat in the past. Patients should not have taken valproic acid for at least 4 weeks prior to enrollment.
- 3.2.3 Inability to take oral medications on a continuous basis.
- 3.2.4 Patients with active brain metastases should be excluded from this clinical trial because of their poor prognosis and because they often develop progressive neurologic dysfunction that would confound the evaluation of neurologic and other adverse events. Patients with previous brain metastases will be eligible if condition is treated and stable for  $\geq 1$  month
- 3.2.5 History of allergic reactions attributed to compounds of similar chemical or biologic composition to SAHA.
- 3.2.6 Uncontrolled intercurrent illness including, but not limited to, ongoing or active infection, symptomatic congestive heart failure, unstable angina pectoris, cardiac arrhythmia, or psychiatric illness/social situations that would limit compliance with study requirements.
- 3.2.7 Pregnant women are excluded from this study because SAHA is a HDAC inhibitor agent with the potential for teratogenic or abortifacient effects. Because there is an unknown but potential risk for adverse events in nursing infants secondary to treatment of the mother with vorinostat, breastfeeding should be discontinued if the mother is treated with vorinostat.
- 3.2.8 Patient is unable or unwilling to abide by the study protocol and to cooperate fully with the investigator or designee.
- 3.2.9 Patient on current therapy with enzyme-inducing anticonvulsants (see [Appendix G](#))

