## Potential for Drug Interactions

Vorinostat has a low propensity to cause or be affected by drug-drug interactions. In vivo animal models and in vitro human systems have demonstrated that the major pathways of metabolism of vorinostat involve glucuronidation, and hydrolysis followed by  $\beta$ -oxidation (Investigator's Brochure, 2009). As vorinostat is not eliminated via cytochrome P450 (CYP) pathways, it is anticipated that vorinostat will not be subject to drug-drug interactions when co-administered with drugs that are known to be CYP inhibitors or inducers. Since vorinostat was neither a potent inhibitor nor an inducer of CYP enzymes, drug-drug interactions caused by vorinostat are not anticipated. Additionally, vorinostat is not recovered intact in urine to any appreciable extent. Therefore, compounds known to affect renal elimination are not expected to affect the pharmacokinetics of vorinostat.

Prolongation of prothrombin time (PT) and International Normalized Ratio (INR) were observed in patients receiving vorinostat concomitantly with coumarin-derivative anticoagulants. Physicians should carefully monitor PT and INR in patients concurrently administered vorinostat and coumarin derivatives.

Vorinostat should not be administered concomitantly with other HDAC inhibitors (e.g., valproic acid) as class-specific adverse reactions may be additive. Severe (Grade 4) thrombocytopenia with associated gastrointestinal bleeding and anaemia has been reported with the concomitant use of vorinostat and valproic acid.

Patients who have received HDAC inhibitors or compounds with HDAC inhibitor like activity, such as valproic acid, for anti-neoplastic therapy should not enroll in vorinostat oncology trials. Patients who have received such agents for other indications, e.g. epilepsy, may enroll on vorinostat trials after a 30-day wash-out period.

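### The advice in Section 2.2 on valproic acid and other HDAC inhibitors reaches the eligibility and treatment sections only in part

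*Combined protocol and SAP*

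**What the plan says.** Section 2.2, under Potential for Drug Interactions, gives three pieces of advice.

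- Combined use: "Vorinostat should not be administered concomitantly with other HDAC inhibitors (e.g., valproic acid"). The reason given is that "Severe (Grade 4) thrombocytopenia with associated gastrointestinal bleeding and anaemia has been reported with the concomitant use of vorinostat and valproic acid".
- Earlier cancer treatment: patients who have had HDAC inhibitors or compounds that act like them, valproic acid included, "for anti-neoplastic therapy should not enroll in vorinostat oncology trials".
- Other uses: "Patients who have received such agents for other indications, e.g. epilepsy, may enroll on vorinostat trials after a 30-day wash-out period".

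Section 3 takes up two items, both in 3.2.2: "Patients may not be receiving any other investigational agents or have received vorinostat in the past", and "Patients should not have taken valproic acid for at least 4 weeks prior to enrollment". On earlier treatment, 3.1.3 says "Any prior number of chemotherapy regimens is allowed". Criterion 3.1.8 deals with current medication: it opens "Eligibility of patients receiving any medications or substances known to affect or with the potential to affect" vorinostat's action or pharmacokinetics, and leaves the decision to the Principal Investigator.

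For the treatment period, 5.1 rules out other agents used against the tumour, and 5.2 leaves supportive care to the treating physician. The interaction text in 7.1 has the coumarin warning that also stands in Section 2.2, but nothing on valproic acid or other HDAC inhibitors. Appendix F sorts anticonvulsants into enzyme inducers and non-inducers, and lists valproic acid among the non-inducers without comment. Exclusion 3.2.9 covers current use of inducers only.

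**The concern.** Site staff screen from Section 3 and manage patients from Sections 5 to 7. Safety advice that stands only in the Background is easily missed there. Two things could follow. A patient whom Section 2.2 says should not join could be enrolled by correct use of Section 3. And a physician could start valproic acid on study for a non-cancer reason without meeting the warning in any section that governs treatment.

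What is at stake is patient safety and consistent eligibility. Low platelets are already in the most frequent category (above 20%) of vorinostat's adverse event table in 7.1, and the reported event on the combination is grade 4 with bleeding. A need for an anticonvulsant is conceivable, since 3.2.4 admits treated, stable brain metastases.

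**Working it through.** No statistical figure is involved, so the check is to take each kind of patient through Section 2.2 and then through the operative sections.

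| Patient | Section 2.2 | Sections 3, 5, 7.1 and Appendix F | Result |
|---|---|---|---|
| A. Earlier cancer treatment with an HDAC inhibitor other than vorinostat, ended more than 4 weeks ago | Should not enroll | 3.2.2 does not name it; 3.1.3 sets no limit on earlier regimens; 3.1.8 concerns current drugs | Admitted: conflict |
| B. Valproic acid taken as cancer treatment, stopped more than 4 weeks ago | Should not enroll | 3.2.2 is satisfied after 4 weeks, whatever the use | Admitted: conflict |
| C. Valproic acid for epilepsy, stopped 28 or 29 days ago | 30 days required | 4 weeks required | Admitted up to 2 days early |
| D. On study, another HDAC inhibitor started against the tumour | Should not be given | Ruled out by 5.1 | Covered |
| E. On study, valproic acid started for a non-cancer reason | Should not be given | 5.1 does not reach it; 5.2 leaves it to the physician; 7.1 is silent; Appendix F has no caution | Only Section 2.2 stops it |

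A and B are real conflicts between two parts of one protocol. E is a gap in carry-over. C is a difference of 30 − (4 × 7) = 2 days and is trivial.

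**How soon case E would be noticed.** Scheduled laboratory visits fall in weeks 2, 4, 5, 7 and 9, each ±1 day (Schema; Section 9, note e). The gaps are (4 − 2) × 7 = 14, (5 − 4) × 7 = 7, (7 − 5) × 7 = 14 and (9 − 7) × 7 = 14 days. From week 9 the gap is 4 × 7 = 28 days. After 2 years on study, note o allows laboratory tests every 6 × 7 = 42 days (±7), and note n allows medication review every 12 × 7 = 84 days (±7). Section 6.2.2 still asks for laboratory values within 72 hours before each cycle, and the documents do not say how this fits with note o.

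**How many patients.** The documents give no number. None of the agents reviewed for this tumour in Section 2.1 is an HDAC inhibitor, which suggests that A is uncommon. Section 2.2 does say that several HDAC inhibitors are in clinical trials, so earlier exposure is possible.

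**Cost of closing the gap.** Appendix F lists 9 non-inducing anticonvulsants. Without valproic acid, 9 − 1 = 8 remain.

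**The case against.** The strongest reply is that the advice is already in the protocol. There is one version of the document for all sites (Section 11.3), Section 2.2 is current text, and 3.2.2 names valproic acid again at entry. This stands for the treatment period. A reader might infer that the protocol permits valproic acid on study, or contradicts itself there. It does neither: no section allows the combination, and the fault is incomplete repetition. Section 2.2 is also worded as advice (should not), so calling it an absolute ban would overstate it.

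A reader might also take Appendix F as a list of approved drugs that steers sites to valproic acid. It is a classification list, reached from an entry criterion about enzyme inducers, and the order of names carries no meaning. A caution there is useful, but the list itself is not wrong.

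Third, the entry change may come too late. The correlative text in the Schema, Section 8 and Appendix I describes scans already obtained and patients already treated, with two partial responses seen. That suggests that accrual is largely or wholly done, although no text says that it is closed. This limits the value of changing 3.2.2; it does not remove the conflict.

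Fourth, there are safeguards: central eligibility verification (4.2), medication review at study visits, a platelet count of at least 100 × 10⁹/L before each new cycle (6.1), and holds for grade 4 thrombocytopenia (6.2.1) and for possibly or probably drug-related grade 3 to 4 events (Schema). They lower the risk. But if verification applies the Section 3 criteria, it would pass A and B, and the platelet rules act only after exposure. Finally, where new seizures reflect progression, vorinostat stops anyway (5.3), which narrows case E further.

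**Conclusion.** The point holds in two parts of different weight.

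- At entry, 3.2.2 conflicts with Section 2.2. Applied as written, it admits patients A and B, who should not enroll under Section 2.2. This part is wrong as written.
- On treatment, the advice against combined use is present but appears only in the Background. Repeating it is a cheap improvement, not the correction of an error.

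Few patients are likely to be affected in either part. This is a judgement, because the documents give neither earlier HDAC-inhibitor exposure nor anticonvulsant use. The entry part has practical value only if enrolment continues.

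A reader might infer that the response rate or the Simon design is affected. The documents do not support that: a treated patient who passes Section 3 counts in the main response analysis under 12.5.2, and the stage sizes and decision rules do not depend on these criteria. The 2-day wash-out difference is trivial, and the citation in 3.2.9 of Appendix G (the 300 mg diary) in place of Appendix F is a clerical slip.

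**What to change.** 1. In 5.2 and 7.1, add: *Valproic acid and other HDAC inhibitors should not be given during vorinostat treatment (see Section 2.2).* In Appendix F, put a caution beside valproic acid that refers to this sentence. This helps anyone still on drug, whether or not enrolment is open.
2. If any enrolment remains, extend 3.2.2 to exclude earlier anticancer treatment with any HDAC inhibitor or compound that acts like one, and set the 30-day wash-out of Section 2.2 where such agents, valproic acid included, were taken for other reasons.
3. In 3.2.9, change the reference from Appendix G to Appendix F.

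The cost is a few lines of amendment, with no added visits or tests and probably negligible loss of accrual. The one clinical downside is one fewer anticonvulsant option, with 8 other non-inducers still listed in Appendix F.

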### **3.3 Inclusion of Women and Minorities**

Both men and women and members of all races and ethnic groups are eligible for this trial.

## **4. REGISTRATION PROCEDURES**

### **4.1 General Guidelines**

Eligible patients will be entered on study centrally at the Karmanos Cancer Institute by the Study Coordinator. All sites should call the Study Coordinator at [contact] to verify agent availability.

Following registration, patients should begin protocol treatment within 72 hours. Issues that would cause treatment delays should be discussed with the Principal Investigator. If a patient does not receive protocol therapy following registration, the patient's registration on the study may be cancelled. The Study Coordinator should be notified of cancellations as soon as possible.

Except in very unusual circumstances, each participating institution will order DCTD-supplied agents directly from CTEP. Agents may be ordered by a participating site only after the initial IRB approval for the site has been forwarded by the Coordinating Center to the CTEP PIO ([contact]) except for Group studies.

### **4.2 Registration Process**

To register a patient, the following documents should be completed by the research nurse or data manager and faxed to [contact] or e-mailed ([contact] ) to the Study Coordinator:

- Copy of required laboratory tests
- Signed patient consent form
- HIPAA authorization form (signed by patient)
- Eligibility screening worksheet
- Registration form

The research nurse or data manager at the participating site will then call [contact] or e-mail ([contact] ) the Study Coordinator to verify eligibility. To complete the registration process, the Coordinator will

- assign a patient study number
- register the patient on the study
- fax or e-mail the patient study number and dose to the participating site
- call the research nurse or data manager at the participating site and verbally confirm registration.

## 5. TREATMENT PLAN

### 5.1 Vorinostat Administration

Treatment will be administered on an outpatient basis. Reported adverse events and potential risks are described in [Section 7](#). Appropriate dose modifications for vorinostat are described in [Section 6](#). No investigational or commercial agents or therapies other than those described below may be administered with the intent to treat the patient's malignancy.

On Day 1 of the first cycle of vorinostat will be initiated on a continuous daily oral regimen at 400mg PO. The dose may be reduced for individual patients in subsequent cycles depending on toxicity (See [Section 6.2.2](#)). Each treatment cycle will consist of 28 days of therapy.

Vorinostat can be taken with food. Patients need to swallow each capsule whole with a full glass of water. Capsules should not be chewed or opened. If a capsule is broken and the powder of the capsules gets on skin, patients should be instructed to wash the exposed area with copious amounts of water and to inform investigator or nurse of the fact.

Patients are required to record their daily dose in a "pills diary". Missed/ skipped pills or vomited doses should not be re-taken. Patients should be instructed to record those pills as missed doses in the diary and to inform investigator or nurse if that happens.

### 5.2 Supportive Care Guidelines

Patients will be permitted to receive appropriate supportive care measures as deemed necessary by the treating physician. The use of prophylactic granulocyte growth factors is not permitted for the first cycle of therapy.

Patients should maintain adequate fluid and food intake because the dose-limiting toxicities related to vorinostat are anorexia, dehydration, diarrhea, and fatigue. In the setting of dysgeusia, popsicles and Gatorade have been found to be useful by some investigators to maintain adequate hydration. Antiemetics, particularly after the first 3 days of therapy, may be required. Patients should also be encouraged to seek a nutritional consult.

Diarrhea: Treat diarrhea promptly with appropriate supportive care, including loperamide. Instruct patients to begin taking loperamide at the first signs of: 1) poorly formed or loose stool, 2) occurrence of more bowel movements than usual in one day, or 3) unusually high volume of stool. Loperamide should be taken in the following manner: 4 mg at first onset of diarrhea, then 2 mg after each unformed stool. Daily dose should not exceed 16 mg/day. Loperamide should not be taken prophylactically. Advise patients to drink plenty of clear fluids to help prevent dehydration caused by diarrhea. Avoid loperamide if there is the presence of blood or mucus in the stool or if diarrhea is accompanied by fever. If grade 3 or 4 diarrhea develops, discontinue further treatment with vorinostat.

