## **6. DOSING DELAYS/DOSE MODIFICATIONS**

### **6.1 Retreatment Criteria**

Prior to administration of each new cycle following cycle one, patients must have recovered the following organ function:

- absolute neutrophil count  $\geq 1.5 \times 10^9/L$
- platelets  $\geq 100 \times 10^9/L$
- creatinine  $\leq 1.5 \times$  upper limit of normal (ULN)
- other drug related toxicity must have recovered to  $\leq$  grade 1 (excluding alopecia, controllable hypertension, leukopenia and lymphopenia)
- total bilirubin WNL
- AST(SGOT)/ALT(SGPT)  $\leq 2.5 \times$  ULN

Patients not fulfilling these criteria should have treatment delayed by 1 week to allow for recovery of organ function. Patients who cannot be retreated within 3 weeks (21 days) of the end of the previous cycle should be removed from study, unless they are deriving benefit. In the later case, a discussion with the PI and/or CTEP senior investigator will ensue.

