### 6.2.2 Dose Modification for Subsequent Cycles

Laboratory parameters should be obtained within 72 hours prior to initiation of the next cycle of therapy.

| Table 3- Dose Reduction for Toxicity (based on events from previous cycle)                                  |  |
|--|--|
| Toxicity  | Dose Reduction*,†  |
| Grade 3/4 Neutropenia associated with fever
and/or
Grade 4 neutropenia
and/or
Grade 4 thrombocytopenia | 1st occurrence:
Reduce by 100 mg/day – 300mg/day (D1-7)
2nd occurrence: 300mg/day (D1-5), with 2 days of rest
3rd occurrence: Off study     |
| Grade 3 nausea, emesis or diarrhea (not controlled by appropriate supportive care measures)                        | 1st occurrence:
Reduce dose by 100 mg/day- 300mg/day (D1-7)
2nd occurrence: 300mg/day (D1-5), with 2 days of rest
3rd occurrence: Off study |
| Other drug-related grade 3/4 non-hematological toxicity**  | 1st occurrence:
Reduce dose by 100 mg/day – 300mg/day (D1-7)
2nd occurrence: 300mg/day (D1-5), with 2 days                                     |

|  |                                      |
|--|--------------------------------------|
|  | of rest
3rd occurrence: Off study |
|--|--------------------------------------|

\* If a patient is experiencing benefits from vorinostat and needs further dose reduction, a discussion will occur between CTEP and the PI.

\*\* Since fatigue can be a symptom of underlying malignancy, dose reductions will only be done if fatigue can be attributed to vorinostat. No dose reductions will be done for alopecia.

† Note: “D1-7” means for 7 contiguous days in a week for ALL the weeks that the patient will be on treatment (i.e, 300mg/day everyday from D1-28, without any days of rest). “D1-5” means for 5 days out of 7 days (i.e., 5 days on treatment/ 2 days of rest in a week) for a cycle of 28 days.

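### Section 5.2 ends vorinostat at the first grade 3 or 4 diarrhoea while Section 6 and the Schema allow reduced-dose treatment to continue, and the only 300 mg diary does not fit the second dose reduction (minor)

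*Combined protocol and SAP*

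**What the plan says.** **Diarrhoea.** The supportive-care paragraph in Section 5.2 gives loperamide advice and closes with "If grade 3 or 4 diarrhea develops, discontinue further treatment with vorinostat". It sets no condition on whether the diarrhoea is controlled, and it mentions neither restart, dose reduction nor Section 6.

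Section 6.2.1 holds vorinostat during a cycle for any grade 4 non-haematological toxicity, and for grade 3 if supportive care cannot control it. Treatment can then restart at a reduced dose once the toxicity is grade 1 or less. Table 3 in Section 6.2.2 has a row for "Grade 3 nausea, emesis or diarrhea (not controlled by appropriate supportive care measures"). Its steps are 300 mg every day, then "2nd occurrence: 300mg/day (D1-5), with 2 days of rest", then "3rd occurrence: Off study". The Schema also allows two reductions for this event. Section 5.1 sends the reader to Section 6 for dose modification, and the Schema's reduction sentence ends with the same cross-reference.

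**Diary.** The Table 3 footnote explains that D1-5 "means for 5 days out of 7 days (i.e., 5 days on treatment/ 2 days of rest in a week"). Two diaries are supplied. Appendix H is for 400 mg. Appendix G, the only one for 300 mg, tells the patient to take three 100 mg capsules every day for 28 days and has 28 dosing rows.

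**Mid-cycle holds.** The Schema withholds the drug for any grade 3 to 4 event possibly or probably related to it. Section 6.2.1 gives a shorter list for drug-related events: grade 4 neutropenia lasting more than 7 days, grade 4 thrombocytopenia, and the two non-haematological triggers above.

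**The concern.** A site cannot end treatment at the first grade 3 or 4 diarrhoea and also restart that patient at 300 mg. The case is foreseeable: Sections 2.2 and 5.2 name diarrhoea as a dose-limiting toxicity. Section 12.1.1 expects that responses may come as late as a year into treatment among stable patients still on drug. A patient stopped under 5.2 would lose the further treatment that Section 6 preserves.

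The diary matters because it is what the patient reads. A patient reaches the second reduction only because toxicity recurred on 300 mg daily. Appendix G would keep that patient on the same dose.

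**Working it through.** **1. The diarrhoea rules side by side**

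| Event | Section 5.2 | Section 6.2.1 | Table 3 | Schema |
|---|---|---|---|---|
| Uncontrolled grade 3, 1st occurrence | End treatment | Hold; restart at reduced dose | 300 mg, 7 days a week | First of two reductions |
| Uncontrolled grade 3, 2nd | Already ended | Hold; restart at reduced dose | 300 mg, 5 days a week | Second of two reductions |
| Uncontrolled grade 3, 3rd | Already ended | No separate rule | Off study | No further reduction without discussion with CTEP |
| Grade 4 | End treatment | Hold; restart at reduced dose | Not in the diarrhoea row; fits "Other drug-related grade 3/4 non-hematological toxicity" if related | Withhold if related; reductions allowed |
| Controlled grade 3 | End treatment | Not among the hold triggers | Not in the diarrhoea row | Withhold if related |

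The first four rows carry the conflict. For uncontrolled grade 3 diarrhoea, 5.2 stops at the first occurrence and Table 3 at the third, two reduced-dose steps later. Which Table 3 row covers grade 4 diarrhoea hardly matters, because all three rows prescribe the same steps.

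**2. Dose per 28-day cycle**

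Inputs: 100 mg capsules (Section 7.1); 400 mg daily at the start (Section 5.1); reductions from Table 3 and its footnote; diary schedule from Appendix G.

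- Start: 4 × 100 mg × 28 = 11,200 mg (112 capsules).
- First reduction: 3 × 100 mg × 28 = 8,400 mg (84 capsules); 8,400 / 11,200 = 75.0% of start.
- Second reduction: 5 × 4 = 20 dosing days and 28 − 20 = 8 rest days; 3 × 100 mg × 20 = 6,000 mg (60 capsules); 6,000 / 11,200 = 53.6% of start.
- Appendix G followed at the second reduction: 8,400 mg. Excess = 8,400 − 6,000 = 2,400 mg (24 capsules); 2,400 / 6,000 = 40%.
- Intended cut from the first to the second step: 2,400 / 8,400 = 28.6%. Cut achieved under Appendix G: 0%.

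At 300 mg a day the patient stays below the 400 mg daily maximum tolerated dose that Section 2.2 gives for continuous dosing.

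**3. The statistical design**

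The Section 12.1.1 design (12 then 17 patients, at least 1 responder in Stage 1, at least 3 of 29 overall) was recomputed exactly. The probability of declaring the drug promising at true response rate p is the sum over x = 1 to 12 of P(X₁ = x) × P(X₂ ≥ max(0, 3 − x)), with X₁ ~ Bin(12, p) and X₂ ~ Bin(17, p).

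- p = 0.05: 0.1480 (plan: 0.15).
- p = 0.20: 0.9005 (plan: 0.90).
- Early termination at p = 0.05: 0.95¹² = 0.5404 (plan: 0.540).

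The stated figures reproduce, and no dose rule enters them. Section 12.5.2 keeps patients with dosing errors in the response analysis.

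**The case against.** **Section 6 is plainly meant to govern.** Sections 5.1 and the Schema point there, and 6.2.1, Table 3 and the Schema all allow treatment to continue. That gives a clear direction, and it is a main reason for rating the point minor. It is still a cross-reference and not a precedence rule, and 5.2 follows it with a specific, unconditional instruction.

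**Discontinue might mean a temporary stop.** That reading would largely reconcile 5.2 with the rest. But the sentence refers to further treatment and gives no restart, so a site could fairly take it as final.

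**A reader might infer three conflicting instructions for loperamide-controlled grade 3 diarrhoea:** stop under 5.2, withhold under the Schema, continue under 6.2.1. The documents do not support the third. Section 6.2.1 lists hold triggers; it does not say that only these count, nor that dosing must go on otherwise.

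**A reader might also infer that the Schema and 6.2.1 contradict each other on holds.** The Schema is broader for drug-related grade 3 events and short grade 4 neutropenia; 6.2.1 has no attribution limit and so also covers unrelated grade 4 non-haematological events. A site satisfies both by holding if either applies. This is uneven drafting. Nor does it imply a full extra cycle of exposure in general. Short grade 4 neutropenia differs by at most about 7 days, since 6.2.1 then holds as well. Only a controlled grade 3 non-haematological event that began on day 1 and lasted throughout could span the cycle. Before the next cycle Section 6.1 applies: "other drug related toxicity must have recovered to" grade 1 or less, and "Patients not fulfilling these criteria should have treatment delayed by 1 week to allow for recovery of organ function".

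**Diary errors would be caught.** The Schema requires compliance assessment at visits, and Appendix G asks for the diary and bottle back at Day 28, when 24 extra capsules should show. This should limit an error to about one cycle while visits are four-weekly. The check is weaker after two years, when the Schema lets visits be 12 weeks apart. The error also requires a site to reduce the dose without explaining the rest days.

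**Little treatment remains to protect.** Section 8 describes enrolment and responses in the past tense, and Section 2.2 places most dose-limiting toxicity in the first month. This stands: the benefit is confined to patients still on drug.

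**Conclusion.** The concern holds, and it is minor. Read literally, Section 5.2 ends treatment at the first grade 3 or 4 diarrhoea, where 6.2.1 allows a restart at a reduced dose. For uncontrolled grade 3, Table 3 and the Schema allow two reductions, and Table 3 goes off study only at the third occurrence. Section 6 is probably what was intended, but no text says so. Appendix G contradicts the second reduction by 2,400 mg per cycle, 40% above the intended dose. That figure assumes an unedited diary followed to the letter with no site instruction on rest days.

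A reader might go further and infer that patients were treated inconsistently or that the efficacy result is at risk. The documents do not support either. They give no grade 3 to 4 diarrhoea rate and no sign that sites diverged, and the Simon design and response analysis are unaffected. What is at stake is safety and exposure for the few patients who reach these steps.

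**What to change.** 1. Replace the last sentence of the 5.2 diarrhoea paragraph with an instruction to hold and modify vorinostat per Section 6 for grade 3 or 4 diarrhoea. If the clinical team wants a permanent stop for this toxicity, keep 5.2 and state the stop in 6.2.1, Table 3 and the Schema. That choice is clinical; the requirement is one rule stated everywhere.
2. Add a 300 mg diary for 5 days on and 2 days off, with the 8 rest days per cycle marked, and label Appendix G for the first reduction only.
3. Optionally, align the Schema's hold sentence with 6.2.1, including the wording on attribution.

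The cost is a small amendment and one new diary page. It adds no patients, visits or procedures and leaves the sample size and analysis as they are.
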